6.2 Laboratory Evaluation

Laboratory testing will be performed at each visit just before IMP administration. Local laboratories will be used to analyse the samples, and the local units will be standardised using SI-units for all reporting of laboratory tests.

Hematology

Hematology test will be performed at screening, treatment visit 1-12, End of Treatment visit, and assessment visit 1-8. The following hematology tests will be performed:

Hematology Test	SI-unit
Hemoglobin	g/L
Leukocytes	10 ⁹ /L
Neutrophils (Differential)	%
Lymphocytes (Differential)	%
Monocytes (Differential)	%
Eosinophils (Differential)	%
Basophils (Differential)	%
Neutrophils (absolute)	10 ⁹ /L
Erythrocytes (absolute)	10 ¹² /L
Platelet	10 ⁹ /L

Biochemistry

Biochemistry test will be performed at screening, treatment visit 1, 4, 8, 12 and End of Treatment visit. The following biochemistry tests will be performed:

Biochemistry Test	SI-unit
Alkaline Phosphatase (ALP)	IU/L
Total Bilirubin	umol/L
Alanine Aminotransferase (ALT)	IU/L
Aspartate Aminotransferase (AST)	IU/L
Creatinine	umol/L
Albumin	g/L

Baseline

For hematology and biochemistry laboratory tests baseline is defined as the sample taken prior to first dose of IMP. In case of missing, the screening measurement will be used instead.

Derived variables

- For all laboratory tests change from baseline will derived for all post-baseline measurements.
- A laboratory value marked as LLOQ or having a registered value <LLOQ will be imputed by LLOQ/2. In case >50% of the values at a timepoint are <LLOQ the mean will be set to LLOQ.

Values outside normal ranges

Laboratory values outside the normal ranges will be flagged in the laboratory report. For each flagged value the Investigator should mark the value as “Clinically Significant” (CS) or “Not Clinically Significant” (NCS).

Data presentations

- Table: for each laboratory test, descriptive statistics of observed values by treatment group, total and by treatment/assessment visit.
- Table: for each laboratory test, descriptive statistics of change from baseline by treatment group, total and by treatment/assessment visit.
- Figure: for each laboratory test, scatterplot (using jitter) of observed values by treatment group and treatment/assessment visit.
- Table: for each laboratory test, number and percentage of patients with clinically significant values outside normal ranges by treatment group and treatment/assessment visit.

All laboratory tests will be listed and patients with clinically significant (according to the Investigator’s criteria) abnormal values (out of normal range reported by the laboratory) will be flagged and listed separately. Significant findings made after drug administration that meet the definition of an AE must be reported under the AE section.

6.3 Blood Manganese

Blood samples will be collected for assessment of manganese (Mn) at screening, treatment cycle 4, 8, 12 and End of Treatment. Blood manganese are available in both ug/L and nmol/L. The latter will be used in the summary tables and listings.

Baseline

Baseline is defined as the measurement at screening.

Derived variables

- Change from baseline will derived for all post-baseline measurements.
- Indicator variable if blood manganese is >2xULN.

Data presentations

- Table: descriptive statistics of observed values by treatment group, total and by treatment visit.
- Table: descriptive statistics of change from baseline by treatment group, total and by treatment visit.
- Figure: scatterplot (using jitter) of observed values by treatment group and treatment visit.
- Table: number and percentage of patients with blood manganese values >2xULN by treatment group and treatment visit.

All blood Mn results for individual patients will be listed and patients with clinically significant (according to the Investigator’s criteria) abnormal values (out of normal range reported by the laboratory) will be flagged and listed separately.

6.4 Brain MRI and Neurologic Examination

Monitoring of increased Mn levels and/or Parkinson-like symptoms will be performed. Any patient who has elevated Mn levels (>2xULN) confirmed by MRI that shows Mn accumulation should be immediately withdrawn from further treatment with the IMP.

Patients that show Mn concentrations $>2xULN$ before Cycle 5 or Cycle 9 will be referred to a brain MRI investigation and a neurological examination. If the MRI is positive (i.e. T1-weighted images (MRI intensity) and T1 images in the globus pallidus), the patient will be discontinued from the study and followed every 3 months until resolution (i.e. MRI intensity is low/none).

Blood for Mn assessment will also be taken in the case of Parkinson-like symptoms. If the Mn level is $>2xULN$, an MRI of the brain should be performed (as above). If the Mn level is $\leq 2xULN$ then the patient can continue in the study according to the protocol.

Any results from MRI scan and neurological examinations following an elevated ($>2x ULN$) blood Mn will be listed per patient.

6.5 Vital Signs

Vital signs variables include:

- Resting pulse (beats per minute)
- Resting systolic blood pressure (mmHg)
- Resting diastolic blood pressure (mmHg)

Baseline

For vital signs baseline is defined as the sample taken prior to first dose of IMP. In case of missing, the screening measurement will be used instead.

Derived variables

For all vital signs change from baseline will derived for all post-baseline measurements.

Data presentations

- Table: for each vital sign variable, descriptive statistics of observed values by treatment group, total and by treatment/assessment visit.
- Table: for each vital sign variable, descriptive statistics of change from baseline by treatment group, total and by treatment/assessment visit.

All vital signs variables will be listed by patient.

6.6 Weight and BMI

Baseline

For both weight and BMI baseline is defined as the sample taken prior to first dose of IMP. In case of missing, the screening measurement will be used instead.

Derived variables

- Body Mass Index (BMI) is calculated as: $\text{Weight (kg)} / \text{Height (m)}^2$.
- For both weight and BMI change from baseline will derived for all post-baseline measurements.

Data presentations

- Table: for both weight and BMI, descriptive statistics of observed values by treatment group, total and by treatment/assessment visit.
- Table: for both weight and BMI, descriptive statistics of change from baseline by treatment group, total and by treatment/assessment visit.

Both weight and BMI will be listed by patient.

6.7 Physical Examination

The number and percentage of patients with abnormal physical examination findings will be presented for each body system by treatment group and total for each visit. Individual patient physical examination data will be listed for all enrolled patients.

Table 5 Physical Examination – Body System Examined

Cardiovascular / Circulatory
Digestive / Excretory
Endocrine
Integumentary / Exocrine
Lymphatic / Immune
Muscular
Nervous
Renal / Urinary
Reproductive
Respiratory
Skeletal

6.8 ECOG Performance Status

The number and percentage of patients in the categories of the ECOG performance status will be presented by treatment group and total for each visit. Individual patient ECOG performance status will be listed for all patients.

Table 6 ECOG Performance Status

Grade	ECOG status
0	Fully active, able to carry on all pre-disease performance without restriction
1	Restricted in physically strenuous activity but ambulatory and able to carry out work of a light or sedentary nature, e.g., light house work, office work
2	Ambulatory and capable of all selfcare but unable to carry out any work activities. Up and about more than 50% of waking hours
3	Capable of only limited selfcare, confined to bed or chair more than 50% of waking hours
4	Completely disabled. Cannot carry on any selfcare. Totally confined to bed or chair
5	Dead

6.9 Overall Response Rate (POLAR-M only)

Patients will be evaluated for response according to RECIST v1.1 guidelines. The overall response rate (ORR) is the best response (CR or PR) recorded during chemotherapy treatment. Overall response data is collected at treatment visits 5, 7, 9, end of treatment, and assessment visits month 3, 6, 9, 12 and 15.

The following categories of the overall response assessment will be recorded:

- CR = Complete Response
- PR = Partial Response
- SD = Stable Disease
- PD = Progressive Disease
- NE = Not Evaluable

Derived variables

Overall response rate (ORR) is defined as the best overall response (CR or PR).

Data presentations

- Table: overall response (OR) - number and percentage of patients by treatment group and treatment/assessment visit.
- Table: overall response rate (ORR) - number and percentage of patients by treatment group and treatment/assessment visit.

Overall response will be listed by patient.

6.10 Progression-Free Survival (POLAR-M only)

Endpoint. Progression-Free Survival (PFS) is defined as the time from the date of randomisation until the date of objectively determined PD (according to RECIST v1.1) or death due to any cause. Patients without objectively determined PD who are alive at the end of the follow-up period (or who were lost to follow up) will be censored on the date of the patient's last complete radiographic tumor assessment. If no baseline or post-baseline radiologic assessment is available, the patient will be censored at the date of randomisation.

Cox Proportional Hazards Model. Time (number of days) from randomisation to event or censoring will be analysed by a cox proportional hazards model using region (Asia / non-Asia) and Treatment as fixed factors in the model. The hazard ratio along with its 95% confidence interval of the PledOx doses compared to placebo will be estimated.

Data presentations

- Table: Progression-free survival based on the cox proportional hazards model will be presented by the number and percentage of events (N, %), Hazard Ratio (95% CI), Minimum, Q1, Median, Q3 and Maximum time to event or censoring by treatment group and total.
- Figure: Progression-free survival will be depicted graphically by a Kaplan-Meier plot by treatment group.

All PFS data will be listed by patient.

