1. INTRODUCTION

The pivotal Phase 3 POLAR program, studying calmagafodipir for the prevention of chemotherapy induced peripheral neuropathy, consists of two studies: POLAR-A and POLAR-M.

- POLAR-A is a placebo controlled, randomised (1:1) Phase III study of calmagafodipir 5 µmol/kg in combination with mFOLFOX6 compared to placebo+mFOLFOX6 in patients with adjuvant treatment of stage III or high-risk stage II colorectal cancer.
- POLAR-M is a placebo controlled, randomised (1:1:1) Phase III study of calmagafodipir in two different doses, 2 µmol/kg and 5 µmol/kg in combination with mFOLFOX6 compared to placebo+mFOLFOX6 in patients with metastatic CRC.

Patient recruitment in the POLAR-A and POLAR-M studies was initiated in late 2018 with the first patient randomised in on January 15, 2019, in POLAR-A and on POLAR-M on January 21, 2019.

On January 23, 2020, the Sponsor announced that the US Food and Drug Administration (FDA) had issued a clinical hold in the US of the POLAR program. The implication was that recruitment and dosing of patients in the POLAR-M study was halted in the US. Based on the evaluation of the independent Drug Safety Monitoring Board (DSMB), the Sponsor's position was that the overall safety profile for PledOx supported the continuation of the POLAR program and both studies continued as planned in Europe and Asia with dosing and further recruitment.

On March 1, 2020, the Sponsor decided to place recruitment and dosing of patients in the POLAR program on hold. The decision followed interactions with the French regulatory authority, ANSM, and the clinical hold issued by the US Food and Drug Administration (FDA) earlier in the year and was due to 4 observed events related to seizure. The Sponsor maintained its position that these events are not related to calmagafodipir, a position which was also supported by the DSMB and an additional independent external evaluation of these cases.

On April 6, 2020, the Sponsor decided to close the POLAR program early with a data cut-off targeted for the third quarter 2020 (further detailed later in this document). The decision was taken after a recommendation from the DSMB to stop the studies due to an accumulation of severe allergic reactions, primarily observed after repeated dosing.

Based on the development of the POLAR studies, a re-assessment of the sample size assumptions is needed to determine a reasonable statistical approach to the analysis of the POLAR studies.

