6.11 Overall Survival (POLAR-M only)

Endpoint. Overall Survival (OS) is defined as the time from the date of randomisation until the date of death from any cause. If the patient was alive at the end of the follow-up period (or was lost to follow-up), the patient will be censored on the last date the patient was known to be alive.

Cox Proportional Hazards Model. Time (number of days) from randomisation to event or censoring will be analysed by a cox proportional hazards model using region (Asia / non-Asia) and Treatment as fixed factors in the model. The hazard ratio along with its 95% confidence interval of the PledOx doses compared to placebo will be estimated.

Data presentations

- Table: Overall survival based on the cox proportional hazards model will be presented by the number and percentage of events (N, %), Hazard Ratio (95% CI), Minimum, Q1, Median, Q3 and Maximum time to event or censoring by treatment group and total.
- Figure: Overall survival will be depicted graphically by a Kaplan-Meier plot by treatment group.

All OS data will be listed by patient.

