6.12 Disease-Free Survival (POLAR-A only)

Endpoint. Disease-Free Survival (DFS) is defined as the time from the date of randomisation until the date of objectively determined signs or symptoms of recurrence of Colorectal Cancer (CRC) or death due to any cause. Signs and symptoms may include any assessment result that, in the opinion of the Investigator, provides evidence for the recurrence of the disease. Patients without objectively determined disease recurrence who are alive at the end of the follow-up period (or who were lost to follow up) will be censored on the date of the patient's last assessment of disease recurrence. If no baseline or post-baseline radiologic assessment is available, the patient will be censored at the date of randomisation.

Cox Proportional Hazards Model. Time (number of days) from randomisation to event or censoring will be analysed by a cox proportional hazards model using region (Asia / non-Asia) and Treatment as fixed factors in the model. The hazard ratio along with its 95% confidence interval of PledOx 5 µmol/kg compared to placebo will be estimated.

Data presentations

- Table: Disease-free survival based on the cox proportional hazards model will be presented by the number and percentage of events (N, %), Hazard Ratio (95% CI), Minimum, Q1, Median, Q3 and Maximum time to event or censoring by treatment group and total.
- Figure: Disease-free survival will be depicted graphically by a Kaplan-Meier plot by treatment group.

All DFS data will be listed by patient.

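### The PFS, OS and DFS tables give the median and quartiles of pooled event and censoring times and no Kaplan-Meier quantile, so these figures understate survival and depend on follow-up.

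*SAP*

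**What the plan says.** SAP sections 6.10 (PFS), 6.11 (OS) and 6.12 (DFS) follow one template. The analysis variable is days from randomisation: "Time (number of days) from randomisation to event or censoring will be analysed by a cox proportional hazards model". The PFS table gives the number and percentage of events, the hazard ratio with its confidence interval, and "Minimum, Q1, Median, Q3 and Maximum time to event or censoring by treatment group and total". OS and DFS use the same list. Each section also plans a Kaplan-Meier plot by treatment group. No section tabulates a Kaplan-Meier median, quartile or confidence interval.

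Censoring differs by endpoint:

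- PFS: a patient without progression who is alive or lost "will be censored on the date of the patient's last complete radiographic tumor assessment".
- PFS and DFS: "If no baseline or post-baseline radiologic assessment is available, the patient will be censored at the date of randomisation".
- OS: "the patient will be censored on the last date the patient was known to be alive".
- DFS: a patient without recurrence "will be censored on the date of the patient's last assessment of disease recurrence".

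Two other places bear on how much censoring there will be. The Introduction records the decision to "close the POLAR program early with a data cut-off targeted for the third quarter 2020", after recruitment and dosing were put on hold on 1 March 2020. Section 2.5 limits analyses and summary tables to data up to 12 months after the first dose and states no exception for the survival endpoints.

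**The concern.** A patient censored at month 2 without progression contributes 2 months to the tabulated quartiles, just as a patient who progressed at month 2 does. A PFS or DFS patient with no radiology contributes 0 days and can set the minimum. Listing a minimum and maximum beside the quartiles, for the same variable that enters the Cox model, shows that raw order statistics are meant and not product-limit quantiles.

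PFS, OS and DFS are listed as safety objectives (sections 2.1.2 and 2.2.2). A per-arm median in a table of progression-free, overall or disease-free survival is easily taken for median survival. The planned figure is not that quantity. It falls as follow-up shortens or early censoring rises, even if the disease course is unchanged.

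**Working it through.** The SAP gives no event count, median or power for these endpoints, so there is no figure of its own to reproduce. The direction of the error needs no assumption. Its size does.

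**Direction.** Let T be the event time and C the censoring time. The tabulated variable is min(T, C), which is never larger than T, so each of its quantiles is at or below the same quantile of T. If C is independent of T, with S(t) = P(T > t) and G(t) = P(C > t), the tabulated median m solves S(m) × G(m) = 0.5. The survival median solves S(m) = 0.5.

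**Inputs.**
- From the Introduction: first POLAR-M randomisation 21 January 2019, recruitment hold 1 March 2020, cut-off targeted for the third quarter of 2020.
- Assumed: even entry and cut-off on 30 September 2020. Potential follow-up is then uniform on 7.0 to 20.3 months (width 13.3).
- Assumed: exponential event times. Where withdrawal is included, it is spread evenly over months 0 to 9.

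**PFS, true median 10 months.** S(t) = 2^(−t/10).
- No withdrawal, t = 8.4: 2^(−0.84) × (20.3 − 8.4)/13.3 = 0.559 × 0.895 = 0.500. The tabulated median is 8.4 months.
- 15% withdrawal, t = 7.5: 0.595 × (12.8/13.3) × (1 − 0.15 × 7.5/9) = 0.595 × 0.962 × 0.875 = 0.501. The tabulated median is 7.5 months.
- Simulation with 1,000,000 patients per case gave 8.39 and 7.50. For true medians of 8 and 12 months without withdrawal it gave 7.52 and 9.07.

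**DFS, assumed 75% event-free at 3 years.** The hazard is −ln(0.75)/36 = 0.00799 per month, so the true median is 0.693/0.00799 = about 87 months. The same calendar is used for POLAR-A, a further assumption.
- t = 12.9: exp(−0.103) × (20.3 − 12.9)/13.3 = 0.902 × 0.556 = 0.502. The tabulated median is 12.9 months, with 10.3% of patients having an event.
- If the 12-month limit in section 2.5 applies: just before 12 months, S × G = 0.909 × (8.3/13.3) = 0.567, still above 0.5. The median therefore sits at the cap, 12.0 months. The PFS figures lie below 12 and do not change.

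**Second calculation, different cut-off.** Follow-up is uniform on 6 to 20 months (cut-off assumed at the end of August 2020), with no withdrawal and 100,000 patients per case.

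| Endpoint | Assumed true median (months) | Events | Raw median | Kaplan-Meier median |
|---|---|---|---|---|
| PFS | 8 / 10 / 12 | 66% / 58% / 51% | 7.1 / 7.9 / 8.5 | 8.0 / 10.0 / 12.0 |
| OS | 18 / 24 / 30 | 39% / 31% / 26% | 9.8 / 10.5 / 11.0 | 18.1 / not reached / not reached |
| DFS | 60 / 100 / 150 | 14% / 9% / 6% | 12.0 / 12.4 / 12.6 | not reached in all three |

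Median potential follow-up here is 13.0 months. The raw DFS median stays near it and moves by 0.6 months while the true median goes from 60 to 150.

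**Dependence on follow-up.** With a true PFS median of 10 months, shortening follow-up from 6–20 to 3–14 months moves the raw median from 7.9 to 5.8. The Kaplan-Meier median stays at 10.0 to 10.1.

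These calculations treat patients without an event or withdrawal as observed to the cut-off. The PFS and DFS rules censor at the last relevant assessment, and some patients at day 0, so the raw times would be shorter still.

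**The case against.** The strongest reply is that the plan handles censoring properly wherever it estimates or compares. The Cox model, the event counts and the Kaplan-Meier curves are all there, and the hazard ratio sits in the same table as the quartiles. The statistic is described for what it is and is never called median survival. Table shells and labels are in a separate output specification, which may make this plainer. The endpoints are safety outcomes outside the formal testing procedure of section 3, which concerns the primary endpoint, and no rule uses the raw median. All of this stands, and it confines the point to a few cells of three tables. It does not make those cells useful as survival summaries.

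A reader might infer more than the SAP supports:

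- *That withdrawn or lost patients are analysed as events.* They are not. They are pooled with events only in the order statistics. Nor is the censoring date generally the last contact; only the OS rule resembles that.
- *That the figure simply measures follow-up.* This is nearly so for DFS. For PFS, half or more of patients have events in the scenarios above, so the figure is a mixture.
- *That it could suggest or hide harm.* Under the first set of assumptions, 15% against 30% withdrawal gives raw PFS medians of 7.5 and 6.5 months, a gap of 1.0 with no true difference. Nothing in the SAP supports such an imbalance. With about 97 patients per arm (290/3), the sampling SD of the difference in raw medians is about 1.05 months. The hazard ratio and curves would also stand beside it.

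**Conclusion.** The point holds as a defect of descriptive reporting in sections 6.10 to 6.12. Followed as written, the per-arm median and quartiles are biased downward as survival summaries for PFS and OS, are close to follow-up time for DFS, and depend on each arm's censoring pattern. The direction follows from the definition. The sizes are illustrations that rest on assumed survival, accrual, cut-off and withdrawal: for PFS about 8.4 or 7.5 months against a true 10, and for DFS about 12 to 13 months (at most about 12 if the section 2.5 limit applies) where no median can be estimated. The Cox hazard ratios, event counts, Kaplan-Meier plots and primary analysis are unaffected.

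**What to change.** In sections 6.10, 6.11 and 6.12, replace the five order statistics with the Kaplan-Meier Q1, median and Q3 and their 95% confidence intervals by arm, printing 'not reached' where that is so. If the raw times are kept, label them as observed follow-up time, not survival. Kaplan-Meier event-free rates at fixed times and reverse Kaplan-Meier follow-up would be useful but are optional.

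The cost is a wording change in three sections and the matching table shells. The Kaplan-Meier fit is already needed for the figures, and no new data are required.

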6.11 Overall Survival (POLAR-M only)

Endpoint. Overall Survival (OS) is defined as the time from the date of randomisation until the date of death from any cause. If the patient was alive at the end of the follow-up period (or was lost to follow-up), the patient will be censored on the last date the patient was known to be alive.

Cox Proportional Hazards Model. Time (number of days) from randomisation to event or censoring will be analysed by a cox proportional hazards model using region (Asia / non-Asia) and Treatment as fixed factors in the model. The hazard ratio along with its 95% confidence interval of the PledOx doses compared to placebo will be estimated.

Data presentations

- Table: Overall survival based on the cox proportional hazards model will be presented by the number and percentage of events (N, %), Hazard Ratio (95% CI), Minimum, Q1, Median, Q3 and Maximum time to event or censoring by treatment group and total.
- Figure: Overall survival will be depicted graphically by a Kaplan-Meier plot by treatment group.

All OS data will be listed by patient.

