2.1.4 Study Design

POLAR-A is a Phase 3, multicenter, double-blind, placebo-controlled study using PledOx for prevention of chronic CIPN induced by oxaliplatin in patients with pathologically confirmed CRC, who are indicated for adjuvant mFOLFOX6 chemotherapy for up to 6 months.

Patients will be randomised in a 1:1 ratio to 1 of 2 treatment arms:

- Arm A: PledOx (5 μ mol/kg) + mFOLFOX6 chemotherapy
- Arm B: Placebo + mFOLFOX6 chemotherapy

Figure 1

$t=0$ (baseline: Day 1, Cycle 1); R=randomization; EoT=end of treatment; DFS=disease free survival

Note: CIPN will be evaluated by the first 4 items of the FACT/GOG-NTX-13 (i.e. FACT/GOG-NTX-4), targeting numbness, tingling or discomfort in hands and/or feet, also at 9, 12, 18 and 24 months after the first dose of IMP

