2.2.2 Secondary Objectives

The secondary objectives of the study are to compare each dose of PledOx vs placebo regarding the following:

Efficacy

- The proportion of patients with mild, moderate or severe chronic CIPN
- The sensitivity to touching cold items
- The cumulative dose of oxaliplatin during chemotherapy
- The vibration sensitivity on the lateral malleolus
- The worst pain in hands or feet
- The functional impairment (in the non-dominant hand)
- The sustained efficacy on prevention of CIPN during long-term follow-up

Safety

- Overall response rate (ORR)
- Progression-free survival (PFS)
- Overall survival (OS)
- Safety and tolerability

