2.2.4 Study Design

POLAR-M is a Phase 3, multicenter, double-blind, placebo-controlled study to establish the efficacious dose of PledOx in prevention of chronic CIPN induced by oxaliplatin. Patients with metastatic CRC, who are indicated for first-line modified FOLFOX-6 (mFOLFOX6) chemotherapy for at least 3 months, without any pre-planned treatment breaks, will be randomised in a 1:1:1 ratio, stratified by region (Asia, non-Asia) and PK sub-study (yes, no), to one of three treatment arms:

- Arm A: PledOx (2 μ mol/kg) + mFOLFOX6 chemotherapy
- Arm B: PledOx (5 μ mol/kg) + mFOLFOX6 chemotherapy
- Arm C: Placebo + mFOLFOX6 chemotherapy

Figure 2. POLAR-M Study Design

t=0 (baseline: Day 1, Cycle 1); R=randomization; EoT=end of treatment; PFS=progression-free survival; OS=overall survival; EoS=end of study

Note: CIPN will be evaluated by the first 4 items of the FACT/GOG-NTX-13 (i.e. FACT/GOG-NTX-4), targeting numbness, tingling or discomfort in hands and/or feet, also at 12, 15, 18, 21 and 24 months after the first dose of IMP

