2.4 Sample Size

As stated in Introduction the dosing of IMP stopped earlier than planned. Hence, the sample size assumptions originally stated in the protocols do not longer hold. In POLAR-A a total of n=301 patients have been randomised as compared to the planned n=280, and in POLAR-M n=290 patients have been randomised as compared to the planned n=420. The sample size protocol text below are stated for reference.

Protocol text (Section 10.2 in the CSPs)

The assumption of the proportion of patients who will satisfy the criteria for the primary endpoint in the untreated (placebo) study population is based on the results in the SCOT trial. Results were presented at ASCO 2017 and roughly 40% of the placebo population had symptoms graded “quite a bit/very much”, which corresponds to 3 or more in this study.

With 112 patients per group, the **POLAR-A** study has 91% power to detect a reduction (improvement) from 40% to 20% (OR = 0.375) in the primary endpoint using two-sided test controlled at the 0.05 type-I error rate. To account for 20% dropout in the study, in total 280 patients (140 patients per arm) will be randomised.

With 112 patients per group, the **POLAR-M** study has 91% power to detect a reduction (improvement) from 40% to 20% (odds ratio = 0.375) in the primary endpoint using two-sided test controlled at the 0.05 type-I error rate. To account for 20% dropout in the study, in total 420 patients (140 patients per arm) will be randomised.

Sample size assumptions will be monitored in a blinded fashion as part of the regular monitoring of the study. In case there are indications these are not met; a re-estimation of the sample size may occur.

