3. GENERAL STATISTICAL PRINCIPLES

Testing Procedure. The formal testing procedure of the primary endpoint is first to perform the analysis on PledOx 5 µmol/kg vs Placebo on both POLAR-A and POLAR-M studies combined. If the results are statistically significant then the same analysis will be performed on the POLAR-A study alone. All tests will be done on the 0.05 level of significance.

Statistical analyses will include stratification factors for study (POLAR-A / POLAR-M) and region (Asia/non-Asia).

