4.3.4 ECOG Performance Status

The number and percentage of patients in the categories of the ECOG performance status (see Table 1) at baseline (time of administration of the first dose of IMP – day 1, cycle 1) will be presented by treatment group and total.

Table 1 ECOG Performance Status

Grade	ECOG status
0	Fully active, able to carry on all pre-disease performance without restriction
1	Restricted in physically strenuous activity but ambulatory and able to carry out work of a light or sedentary nature, e.g., light house work, office work
2	Ambulatory and capable of all selfcare but unable to carry out any work activities. Up and about more than 50% of waking hours
3	Capable of only limited selfcare, confined to bed or chair more than 50% of waking hours
4	Completely disabled. Cannot carry on any selfcare. Totally confined to bed or chair
5	Dead

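### The PFS, OS and DFS Cox models leave out baseline ECOG status, which is already collected; pre-specifying it would be a small, nearly free gain in precision, not the repair of an invalid analysis.

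*SAP*

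**What the plan says.** PFS and OS in POLAR-M (Sections 6.10 and 6.11) and DFS in POLAR-A (Section 6.12) are each specified in the same words. The event time, in days since randomisation, "will be analysed by a cox proportional hazards model using region (Asia / non-Asia) and Treatment as fixed factors in the model". The output is an estimate with an interval; for PFS and OS, "The hazard ratio along with its 95% confidence interval of the PledOx doses compared to placebo will be estimated". A Kaplan-Meier plot accompanies each. No test, margin, event target or power is attached to any of the three. They are listed among the secondary safety objectives (Sections 2.1.2 and 2.2.2).

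On ECOG, Section 4.3.4 presents "The number and percentage of patients in the categories of the ECOG performance status (see Table 1) at baseline", by treatment group and total. No model in the SAP uses it.

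On covariates generally, Section 3 says "Statistical analyses will include stratification factors for study (POLAR-A / POLAR-M) and region (Asia/non-Asia". POLAR-M randomisation was "stratified by region (Asia, non-Asia) and PK sub-study (yes, no"; ECOG is not among those factors. For POLAR-A, Section 2.1.4 says "Patients will be randomised in a 1:1 ratio to 1 of 2 treatment arms" and names no stratification factor.

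**The concern.** The three Cox hazard ratios are the only modelled between-arm comparisons of tumour outcome in the SAP; the response rate in Section 6.9 is tabulated only as counts and percentages. Three things follow if ECOG predicts progression, recurrence or death and is left out:

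- The hazard ratio is non-collapsible. When treatment truly has an effect, the ratio not conditional on ECOG lies nearer to 1 than the ECOG-conditional ratio, even with perfectly balanced arms.
- Some power to see a difference is lost.
- A chance imbalance in ECOG between arms stays in the estimate. Adjusting for it after unblinding would be post hoc.

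For a safety outcome, moving toward no difference is the less welcome direction. Information is also limited: POLAR-M stopped at 290 of the 420 planned patients, and Section 2.5 limits analyses to 12 months after first dose.

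**Working it through.** **The plan's own figure.** The only power statement is for the primary CIPN endpoint: 112 per group, 40% versus 20%, two-sided 0.05. With a pooled rate of 0.30, z = (0.20·√112 − 1.96·√(2·0.30·0.70)) / √(0.40·0.60 + 0.20·0.80) = (2.117 − 1.270)/0.632 = 1.34, so power is 0.910. The stated 91% reproduces. There is no corresponding figure for PFS, OS or DFS to check.

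**Inputs from the SAP.** Section 2.4 gives the numbers randomised: "In POLAR-A a total of n=301 patients have been randomised as compared to the planned n=280, and in POLAR-M n=290 patients". For one POLAR-M dose against placebo, 290 × 2/3 ≈ 193 patients. For POLAR-A, 301. Section 6 uses the safety set, which for POLAR-M is 285 dosed patients (Section 1, Table 1), or 285/3 = 95 per arm. Using 190 instead of 193 changes power trivially (0.424 versus 0.429 at 40% events).

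**Assumptions, none in the SAP.** True ECOG-conditional treatment hazard ratio 1.5; ECOG 1 or higher in 30% to 50%; ECOG hazard ratio 1.5, 2 or 3; event fraction 15%, 40% or 70%; exponential hazards with a common censoring time.

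**Step 1: hazard ratio without ECOG.** Within each arm survival is a mixture over ECOG, S(t) = (1 − p)·exp(−ht) + p·exp(−hgt), where p is the ECOG prevalence, g the ECOG hazard ratio and h the arm's hazard at ECOG 0. The limiting treatment-only Cox estimate is the b that solves ∫[d₁ − (d₁ + d₀)·eᵇS₁/(eᵇS₁ + S₀)] dt = 0, with d₁ and d₀ the event densities in the two arms.

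**Step 2: power.** Power = Φ(|ln HR|·√(d/4) − 1.96), with d = N × event fraction. Example, N = 193 and 40% events: d = 77.2. With HR 1.5, 0.4055 × 4.393 − 1.96 = −0.179, so power is 0.429. With HR 1.4836 (ECOG HR 2, prevalence 50%), 0.3945 × 4.393 − 1.96 = −0.227, so power is 0.410.

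Results for a true HR of 1.5 and ECOG prevalence 50%:

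| ECOG HR | Events | HR without ECOG | Power, N = 193 (true HR → HR without ECOG) |
|---|---|---|---|
| 1.5 | 40% | 1.494 | 0.429 → 0.422 |
| 1.5 | 70% | 1.488 | 0.654 → 0.637 |
| 2 | 40% | 1.484 | 0.429 → 0.410 |
| 2 | 70% | 1.466 | 0.654 → 0.603 |
| 3 | 40% | 1.461 | 0.429 → 0.385 |
| 3 | 70% | 1.418 | 0.654 → 0.528 |

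For DFS with N = 301 and 15% events, the largest loss over the grid is at ECOG HR 3 and prevalence 30%: HR 1.4845, power 0.275 → 0.264.

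**Step 3: simulation check.** With 2,000 replicates per scenario, region in both models and ECOG prevalence 50%:

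| N, events, ECOG HR | Mean HR with / without ECOG | Power with / without ECOG |
|---|---|---|
| 194, 40%, 2 | 1.516 / 1.495 | 0.429 / 0.408 |
| 194, 70%, 2 | 1.500 / 1.460 | 0.642 / 0.591 |
| 194, 70%, 3 | 1.497 / 1.418 | 0.635 / 0.524 |
| 301, 15%, 2 | 1.519 / 1.513 | 0.260 / 0.253 |

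With a true HR of 1, neither model shifts (mean HR 0.99 to 1.00) and rejection is 4% to 6% either way.

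**Step 4: chance imbalance.** With 95 per arm and 40% at ECOG 1 or higher (assumed), the standard deviation of the between-arm difference is √(2 × 0.4 × 0.6/95) = 0.071, or 7 points. At ECOG HR 2 a one-SD imbalance moves the log hazard ratio by about 0.071 × ln 2 = 0.049, roughly 5%.

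**Scale.** At N = 194 and 40% events the standard error of the log hazard ratio is about 0.23, so each 95% limit lies a factor exp(1.96 × 0.23) ≈ 1.57 from the estimate. The shifts above are small beside that.

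**The case against.** The strongest reply is that the plan makes no error here. Section 3 calls for the stratification factors study and region; each Cox model covers one study, so region is what remains, and Sections 6.10 to 6.12 follow the rule. Under randomisation the region-only model is valid and simply targets a different hazard ratio. The gain is small beside sampling error and close to nil for DFS, and scarce events limit these analyses far more than one covariate does. Imbalance will be visible in the baseline ECOG table. All of this stands, and it is why the point is minor.

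What does not stand is the inference that Section 3 rules ECOG out. The SAP's ANCOVAs add baseline covariates (for example Sections 5.3.4 to 5.3.6), and the POLAR-M Cox models omit PK sub-study, which was a randomisation factor. It is fair to say that the ANCOVA covariate is the baseline of the same outcome, which a time-to-event endpoint lacks; that weakens the analogy but does not bar a prognostic covariate. Seeing an imbalance in a table also does not correct it.

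A reader might infer more: that the plan biases the hazard ratios so as to hide harm, or that these models must prove that PledOx does not weaken the chemotherapy. The SAP supports neither. Nothing shifts under the null, the difference under an effect is one of estimand, and the SAP sets these endpoints no hypothesis, margin or power that could be lost.

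**Conclusion.** The point holds as a minor improvement. All three models adjust only for region while a baseline factor that is plausibly prognostic is collected and left unused.

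How much this matters cannot be derived from the SAP. Under a true hazard ratio of 1.5 and a moderate ECOG effect (hazard ratio 1.5 to 2), the unadjusted ratio is about 1.46 to 1.50 and the power loss is 0 to 5 points. A strong ECOG effect (hazard ratio 3) with 70% events gives about 1.42 and about 13 points, the worst case examined. For DFS at 15% events the loss is about 1 point at most. If ECOG is not prognostic, hardly varies, or treatment has no effect, there is no systematic shift.

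**What to change.** At the blind review, before unblinding, change the model statement in Sections 6.10, 6.11 and 6.12 so that baseline ECOG, coded 0 versus 1 or higher, is a fixed factor alongside region and treatment. Keep the region-only model as a named sensitivity analysis, and state that the main hazard ratio is then conditional on ECOG.

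Disease stage should not be added to the DFS model on this argument: the SAP names stage in describing the POLAR-A population, but no section lists or derives it as an analysis variable.

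The cost is one line of wording and one extra term per model, using data already collected. The gain will be slight if ECOG varies little or events are few.
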